## 21. Other assessments

The following assessments will only be presented in data listings for the SAF population:

### 21.1 Physical examination data

A complete physical examination will be performed at screening (Visit 1). Physical examinations will be performed by a physician.

A full physical examination will include the following: evaluation for jaundice, pallor (anemia), cyanosis, clubbing, edema, and lymphadenopathy; skin evaluation: fundoscopy; ear, nose, and throat; cardiovascular assessment; respiratory assessment; abdominal examination; musculoskeletal assessment; neurological assessment. Other evaluations may be performed as deemed necessary by the Investigator.

Clinically significant findings must be recorded as AEs.

Physical examination data will be presented classified as normal or abnormal.

### 21.2 Electrocardiograms

A 12-lead, resting ECG will be obtained at the timepoints indicated in the schedule of assessments (Section 4.2; Protocol NKF-INS(A)-101, Version 2.0, dated 06-May-24). ECG should always be performed after the participant has been resting in a supine position for at least 5 minutes.

The frequency of abnormalities (e.g., heart rate, PR interval, QRS complex, and QTcF [Fridericia's corrected QT]) will be summarized by treatment group and scheduled visits using counts and percentages.

---

An assessment of normal, abnormal clinically significant, or abnormal not clinically significant will be recorded; if the ECG is considered abnormal, the abnormality will be documented in the eCRF. ECGs may be repeated if clinically significant abnormalities are observed, or artifacts are present. Any confirmed, clinically significant abnormal ECG findings must be recorded as AEs.

Participant ECG status (normal, abnormal clinically significant, or abnormal not clinically significant) may be summarized for each scheduled ECG and shifts from screening may be tabulated. Raw data and derivations will also be presented as a listing for the SAF population. Data will be analysed as outlined in ICH E14.

Abnormal ECG values will be identified in accordance with the following predefined normal criteria:

- PR Interval: 120 to 220 (msec)
- QRS Duration: < 120 (msec)
- Heart rate: 50 to 100 (bpm)
- QTc Interval: 350 to 450 (msec)
- For the QT, QTcF parameters, the following categorisations will be done:
  - $x \leq 450$  ms (considered as normal range)
  - $450 < x \leq 480$  ms
  - $480 < x \leq 500$  ms
  - $x > 500$  ms

and for change from baseline:

- $x \leq 30$  ms (considered as normal range)
- $30 < x \leq 60$  ms
- $x > 60$  ms
- For the PR parameter, the following categorisations will be done:
  - $x < 120$  ms
  - $120 \leq x \leq 220$  ms (considered as normal range)
  - $x > 220$  ms
- For heart rate, the following categorisations will be done:
  - $x < 50$  bpm
  - $50 \leq x \leq 100$  bpm (considered as normal range)
  - $x > 100$  bpm

## 21.3 Injection site assessment

The injection site and surrounding area will be assessed by the investigator at 1 min and 15 min post-dose on Day 1 and at the EOS visit. Reactions to the study drug injection will be documented using a numerical scoring system. The injection site assessment will be summarised (frequency and percentage) by type of assessment and timepoint for the SAF population. The injection site assessment will be listed for the SAF population.

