Safety	Safety assessments include vital signs, physical examinations, ECG recordings, clinical laboratory assessments (hematology, clinical chemistry [including glucose], coagulation, and urinalysis), AE monitoring (including injection site reactions). AEs will be coded by using the Medical Dictionary for Regulatory Activities dictionary. All treatment-emergent AEs (TEAEs) will be summarized by insulin product (NKF-INS(A), US-NovoLog®, EU-NovoRapid®) as follows: 
• All AEs• Grade ≥ 3 AEs• AEs related to study treatment, including related Grade ≥ 3 AEs• All adverse reactions• Serious AEs (SAEs) All AE data will be defined in the listing (onset, stop date, severity, etc.). The original results and change from baseline values for clinical laboratory assessments, vital signs, and ECG parameters, will be summarized by insulin product and scheduled visits. Potential clinically significant values will also be flagged and summarized. Significant changes in physical examination findings will be listed as AEs. Injection site reactions will be summarized by treatment group and scheduled visits. The number and percentage of participants having reactions at each assessment timepoint, overall and by specific reaction subtype, will be presented.
Other Assessments	Not applicable
Statistical Methods and Planned Analyses	The statistical evaluation will be performed using R version 4.0 or higher. All data will be listed, and summary tables and figures will be provided. Summary statistics will be presented by treatment group, to the extent possible. For continuous variables, data will be summarized with the number of participants (N), arithmetic mean, standard deviation (SD), median, minimum, and maximum by treatment group. Geometric mean and coefficient of variation (CV%) will be presented as appropriate, by treatment group. For categorical variables, data will be tabulated with the number and proportion of participants for each category by treatment group.
Interim Analysis	Not applicable.

Data Monitoring Committee	Not applicable.
----------------------------------	-----------------

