14.5. Safety Analysis

All analyses of safety will be conducted on the Safety Population unless otherwise specified in the SAP.

All reported AEs will be graded using NCI CTCAE version 5.0 and will be coded using the Medical Dictionary for Regulatory Activities, version 26.0. The incidence of treatment-emergent AEs (TEAEs) will be included in incidence tables. Events with missing onset dates will be included as treatment-emergent. If a participant experiences more than 1 occurrence of the same AE, the occurrence with the greatest severity and the closest association with the study treatment will be used in the summary tables. All TEAEs will be summarized by treatment group (NKF-INS(A), US-NovoLog®, and EU-NovoRapid®) as follows:

- All AEs
- Grade ≥ 3 AEs
- AEs related to study treatment, including related Grade ≥ 3 AEs
- All adverse reactions
- SAEs

All AEs will be listed by participant, along with information regarding onset, duration, relationship and severity to study treatment, action taken with study treatment, treatment of event, and outcome.

Clinical laboratory data (hematology, clinical chemistry [including glucose], coagulation, and urinalysis) and vital signs (heart rate, respiratory rate, systolic and diastolic blood pressure, and temporal or ear temperature measurements) will be summarized by treatment group and

scheduled visits using descriptive statistics, including mean values and mean change from screening values, as well as numbers of participants with values outside limits of the normal range at each timepoint. Shift tables will be provided presenting change from screening values to the last EOS visit.

The frequency of ECG abnormalities (e.g., heart rate, PR interval, QRS complex, and QT-interval corrected by Fridericia's formula [Fridericia's corrected QT]) will be summarized by treatment group and scheduled visits using counts and percentages.

Participant ECG status (normal, abnormal clinically significant, or abnormal not clinically significant) may be summarized for each scheduled ECG and shifts from screening may be tabulated.

Injection site reactions will be summarized by treatment group and scheduled visits. The number and percentage of participants having reactions at each assessment timepoint, overall and by specific reaction subtype, will be presented.

Summary tables will be provided for concomitant medications initiated during the study period.

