**8. Output presentations**

Summary tables will be stratified by treatment sequence randomized to, unless otherwise specified.

The templates provided in the separate output templates document describe the format and content for presentation of tables, listings and figures (TLFs).

Categorical variables will be summarized and presented with the following nomenclature: n = frequency and % = percentage. Categories of NOT REPORTED, MISSING, and/or UNKNOWN may be excluded from summaries if null (0)

For continuous variables, data will be summarized with the number of participants (N), arithmetic mean, standard deviation (SD), minimum, median and maximum by treatment group.

All percentages (%) for a specific summary are calculated using the total number of participants included in the relevant analysis population as the denominator, unless otherwise specified. Tables will summarize relevant data from the eCRF.

Data listings will be based on all participants randomized to IP, unless otherwise specified.

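### The SAP does not state the by-product split that the protocol requires for injection-site scores, vital signs and the TEAE overview; as worded, the injection-site table would mix products unless period is added

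*SAP*

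**What the plan says.** **Protocol.** Section 14.5 takes the three products as the treatment groups. On adverse events: "All TEAEs will be summarized by treatment group". On injection sites: "Injection site reactions will be summarized by treatment group and scheduled visits". For laboratory data and vital signs it asks for summaries by treatment group and visit, including "numbers of participants with values outside limits of the normal range at each timepoint". The synopsis says that "vital signs, and ECG parameters, will be summarized by insulin product and scheduled visits". Section 14 lets the SAP override the protocol where they differ.

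**SAP.**
- Section 8, default for tables: "Summary tables will be stratified by treatment sequence randomized to, unless otherwise specified". The same section also says that continuous variables are summarised by treatment group.
- Section 21.3, injection site: "The injection site assessment will be summarised (frequency and percentage) by type of assessment and timepoint for the SAF population". It also requires a listing. The timepoints are 1 and 15 minutes after dosing, and the end-of-study (EOS) visit.
- Section 21, lead-in to 21.1 to 21.3: "The following assessments will only be presented in data listings for the SAF population". Section 21.3 contradicts this, and so does 21.2, where ECG abnormalities "will be summarized by treatment group and scheduled visits using counts and percentages".
- Section 20.2, vital signs: by treatment sequence and visit.
- Section 18.2, TEAE overview: by treatment sequence and period of event.
- Sections 18.2.1 to 18.2.6, detailed TEAE tables: by treatment of event. Section 18.2.3 defines this as the last treatment received before onset.
- Section 5.3: analyses on the safety set reflect the product actually given, whatever the randomization list says.

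**The concern.** Safety of NKF-INS(A) is a secondary objective, and a descriptive safety comparison in a crossover needs a column for each product. The protocol asks for one in all three summaries. The SAP replaces it with sequence-based groupings in two of them and is silent in the third. Neither SAP 1.1, which says the SAP describes the analyses as the protocol specifies them, nor the revision history explains the change.

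The injection-site table matters most. A reaction minutes after injection belongs clearly to one product, and the protocol amendment added injection-site reactions to the safety endpoint on a regulator's recommendation. A programmer who followed 21.3 and the Section 8 default literally would produce a table in which a difference between products could not be seen.

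**Working it through.** There is no planned figure to reproduce. The check is which groupings isolate a product.

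**Inputs.** Three products, three periods and six sequences allocated equally; 54 participants planned and at least 36 evaluable (protocol synopsis and 14.1). The design figure is not available, so the six sequences are assumed to be the 3! = 6 possible orders.

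**Injection site, sequence without period.** Each sequence contains all three products.
- 54 completers: 54/6 = 9 participants per sequence, so 9 × 3 = 27 scores per row at each of 1 and 15 minutes, 9 per product. In total 54 × 3 = 162 scores per timepoint, 54 per product.
- 36 completers: 36/6 = 6 per sequence, so 18 scores per row, 6 per product. In total 108 scores, 36 per product.

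If all doses are given and there is no sequence effect, the expected rate in every row is (p_test + 2 × p_ref)/3. The documents give no reaction risks, so the values below are assumptions. The reference risk is held at 2%.

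| Assumed NKF-INS(A) risk | Expected rate in every sequence row |
|---|---|
| 6% | (6 + 2 + 2)/3 = 3.3% |
| 10% | (10 + 2 + 2)/3 = 4.7% |
| 20% | (20 + 2 + 2)/3 = 8.0% |

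At 10% against 2%, a product table would show about 0.10 × 54 = 5.4 of 54 against 0.02 × 54 = 1.1 of 54. In the sequence table all six rows have the same expectation. If no stratum is used at all, the single pooled row has that value too.

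**Injection site, sequence with period.** This gives 6 × 3 = 18 cells, each holding one product. Products are then not mixed, but the column the protocol asks for is still absent.

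**Vital signs (sequence by visit).** The clamp visits are numbered 3, 5 and 7 for Periods 1, 2 and 3 (SAP Table 6.1), so each dosing-visit cell holds one product. Each product is spread over 6 of the 18 cells, with 9 participants per cell at 54 completers and 6 at 36. Means, counts and extremes can be recombined into product figures; medians cannot. SAP 20.2 names visits but not time points, whereas SAP 19.2 names both for laboratory tests.

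**TEAE overview (sequence by period).** Again there is one product per cell. A participant falls in one cell per product, so counts add exactly across the 6 cells. Sections 18.2.1 to 18.2.6 already give by-product tables by system organ class and preferred term, with separate tables for severity, relatedness, seriousness, withdrawal and death.

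**The case against.** The strongest reply is that SAP 21.3 is silent rather than wrong. It does not say that products are pooled. It refers to the safety set, for which SAP 5.3 says analyses follow the product actually given. The Section 8 default yields wherever something else is specified, and Section 8 itself mentions treatment group for continuous variables. The SAP is meant to complement the protocol, so its silence could leave the protocol's split in force. The separate output templates are not among the documents and may already have product columns.

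Much of this stands. A reader might infer that the SAP certainly produces a pooled injection-site table, or that product-level injection-site information is lost. The documents support neither. Mixing follows only if period is not a table dimension, which the text leaves open, and 21.3 keeps every assessment in a listing.

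A reader might also infer that by-product comparison of vital signs and adverse events has been abandoned. That fails too, because their cells hold one product each and the detailed TEAE tables are by product.

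The reply does not remove the point. SAP 5.3 says which product counts as received; it does not say that tables are split by product. Where the SAP wants period, visit or treatment group as a dimension, it says so (18.2, 20.2, 21.2), and 21.3 does not. A listing is not the count-and-percentage summary by product that the protocol asks for. Templates with product columns would still have to agree with the SAP text.

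**Conclusion.** The concern holds as a minor mismatch between the documents. All three summaries lack the product split that the protocol requires, and the mismatch differs in weight:

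- **Injection site:** the 1- and 15-minute table, as worded and under the Section 8 default, would mix products in every row unless period is added. This is the only one of the three where a product difference could be hidden in the table itself.
- **Vital signs:** the product column is missing but can be partly rebuilt.
- **TEAE overview:** a layout difference, largely covered by tables elsewhere in the SAP.

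The contradiction between the Section 21 lead-in and Sections 21.2 and 21.3 is plain on the page.

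The row figures assume six distinct orders, complete dosing and no sequence effect. The reaction risks are illustrative. One product per cell also assumes no dosing errors, since the SAP groups by randomized sequence. The effect is on descriptive safety tables only; the primary PK/PD analyses, alpha, power and sample size are untouched.

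**What to change.** Amend the SAP before unblinding:

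1. **21.3:** summarise the 1- and 15-minute injection-site scores by treatment received, type of assessment and timepoint. Each product column then has up to 54 injections (36 at the evaluable minimum). Keep the EOS assessment as a separate overall summary not attributed to a product, because it follows all three.
2. **20.2:** summarise vital signs by treatment received and scheduled time point, pre-dose and end of clamp. Body temperature is pre-dose only, because Protocol Table 3 (note 9) does not schedule it at the end of the clamp.
3. **18.2 overview:** use treatment of event as already defined in 18.2.3.
4. **21 lead-in:** limit the listings-only sentence to physical examination (21.1).

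Laboratory summaries (SAP 19.2) are also by sequence, but those tests are scheduled only at screening or at screening and EOS. A product split would mean little there, and they can be left alone.

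The cost is SAP wording and minor table-shell work. All the data are already collected. If the output templates already show product columns, only the text changes.

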## 22. Pharmacokinetic Analysis

The primary PK objective of this trial is to compare the PK of NKF-INS(A) to US-approved (US-NovoLog®) and EU-authorized (EU-NovoRapid®) insulin to demonstrate PK similarity for insulin aspart. The secondary PK objective is to evaluate additional PK parameters NKF-INS(A) compared to US-approved and EU-authorized insulin aspart. Details on the endpoints are provided in Section 3.

PK concentrations and parameter data will be listed and summarized descriptively (N, arithmetic and geometric mean, SD, CV%, median, minimum and maximum) and graphically by treatment.

Biosimilarity between the test product and the US-approved and EU-authorized insulin aspart will be considered separately, i.e., test product vs US-approved product and test product vs EU-authorized product. Biosimilarity of the test and reference products will be assessed on the basis of 90% CIs for estimates of the geometric mean ratios between the primary PK parameters of the test and reference products in relation to the conventional bioequivalence range of 80% to 125%.

Due to different regulatory requirements in terms of preferred statistical methods used in bioequivalence assessment, the test and respective reference insulin products will be analysed using two statistical models. Briefly, the Test-EU Reference comparison will be analysed using a model that only includes fixed effects and the Test – US-reference comparison will be analysed using a mixed effects model that includes both fixed and random effects.

### 22.1 Pharmacokinetic Concentrations

All PK blood sampling times, including time deviations, will be listed for all participants in the SAF population (to ensure data for participants excluded from the PK population are listed).

For geometric statistics, imputed BLQ values of zero will be omitted. In addition, the percentage and number of participants, with plasma concentrations below the BLQ will be presented at each timepoint. Natural log transformations will be used throughout the analysis, where applicable. CV% will be calculated as follows:

$$\text{Arithmetic CV\%} = \left( \frac{\text{arithmetic standard deviation}}{\text{arithmetic mean}} \right) * 100$$

$$\text{Geometric CV\%} = (\sqrt{\exp(\text{variance}) - 1}) * 100$$

All PK concentration data will be listed for all participants in the SAF population (to ensure data for participants excluded from the PK population are listed).

### 22.2 Pharmacokinetic Parameters

The PK parameters will be derived for NKF-INS(A), US-NovoLog®, and EU-NovoRapid® from serum concentrations by a validated PK analysis using linear up/ linear down non-compartmental analysis (NCA) (where data allow). A description of the PK parameters is provided in Table 22.2:

*Table 22.2: PK Parameters and their descriptions.*

PK Parameter	Description
$AUC_{0-4h}$	concentration-time curve from 0 to 4 hours
$AUC_{0-6h}$	concentration-time curve from 0 to 6 hours
$AUC_{6-12h}$	concentration-time curve from 6 to 12 hours
$AUC_{0-12h}$	concentration-time curve from 0 to 12 hours/end of clamp
$AUC_{0-t}$	concentration-time curve from 0 hour to the last quantifiable concentration time
$AUC_{0-\infty}$	concentration-time curve from 0 hour to infinity
$T_{max}$	time to maximum serum concentration
$C_{max}$	maximum observed insulin aspart concentration
$t_{50\%-\text{early}}$	time to half-maximum before $C_{max}$
$t_{50\%-\text{late}}$	time to half-maximum after $C_{max}$
$t_{1/2}$	terminal elimination half-life

PK parameters will be estimated using non-compartmental analysis. Estimates of PK parameters will be listed and summarized (N, arithmetic and geometric mean, SD, CV%, median, minimum, and maximum) by treatment, descriptively and graphically.

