Planned Sample Size	54 healthy male participants are planned to be enrolled in the study to have at least 36 evaluable participants.
Investigational Therapy	NKF-INS(A) administered as a 0.3 U/kg single SC dose in the perumbilical area.
Reference Therapy	EU-NovoRapid® and US-NovoLog®, both administered as a 0.3 U/kg single SC dose in the perumbilical area.

Treatment Duration	The study will consist of a screening period of up to 4 weeks (Days -28 to -1), three treatment periods each consisting of 1-day dose administrations and euglycemic clamp periods (periods 1, 2, and 3) separated by a washout period of 3-14 calendar days between treatment periods 1 and 2, and a washout period of 5-21 calendar days between treatment periods 2 and 3, and a follow-up period of 2-11 days. The entire study duration will be a maximum of 11 weeks.
Pharmacokinetics	Insulin (serum) samples will be collected at 60, 30, 0 minutes pre-dose and 5, 10, 20, 30, 40, 50, 60, 75, 90, 105, 120, 135, 150, 180, 210, 240, 300, 600, and 720 minutes post-dose.
Pharmacodynamics	C-peptide (serum) 60, 30, 0 minutes pre-dose and 5, 10, 20, 30, 40, 50, 60, 75, 90, 105, 120, 135, 150, 180, 210, 240, 300, 600, and 720 minutes post-dose. Blood glucose values will be analyzed pre-dose, every 3 minutes from 0 to 120 minutes, every 5 minutes from 120 to 240 minutes, and every 10 minutes from 240 to 720 minutes post-dose.
Immunogenicity	Not applicable

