## 3. End points

### 3.1 Primary endpoints

- Aspart concentration-time curve from 0 to 12 hours (AUC0-t).
- Maximum observed insulin aspart concentration (Cmax).

- Area under the GIR-time curve from 0 to 12 hours (AUCGIR0-t).
- Maximum GIR (GIRmax) of glucose.

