### 3.2 Secondary endpoints

- PK parameters for serum insulin aspart concentrations: AUC0-4h, AUC0-6h, AUC6-12h, AUC0-12h, Tmax, AUC0-∞.
- Time to half-maximum before Cmax (t50%-early).
- Time to half-maximum after Cmax (t50%-late).
- The terminal elimination half-life (t1/2).
- AUCGIR from 0 to 4 hours (AUCGIR0-4h), from 0 to 6 hours (AUCGIR0-6h), and from 6 hours until the end of clamp (AUCGIR6-last).
- Time to maximum GIR (Tmax.GIR).
- Time to half-maximum glucose infusion rate before GIRmax (tGIR, 50%-early).
- Time to half-maximum glucose infusion rate after GIRmax (tGIR, 50%-late, indicator of end of duration of action).
- Time from study drug administration until the blood glucose concentration has decreased by at least 5mg/dL from baseline (onset of action).
- The difference between tGIR, 50%-late and the onset of action (duration of action).
- AE assessments (including injection site reactions), clinical laboratory investigations (hematology, clinical chemistry, [including glucose], coagulation, and urinalysis), vital signs, physical examinations, 12-lead ECG, prior and concomitant medication assessments.

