## 22.4 Bioequivalence assessment (US)

As specified by *Guidance for industry: Statistical Approaches to Establishing Bioequivalence* [4] the test product will be compared to the reference product by means of statistical analysis with respect to the primary PK parameters using a linear mixed effects model following logarithmic transformation of the data. PK parameters will be estimated using treatment, period and sequence as fixed effects and participants as random effects. A difference in test and reference means and accompanying 90% CI will be back transformed from the log scale to provide estimates of the test/reference ratio of geometric means. Inter- and intra-subject variability will be estimated from the linear mixed effects model.

Point estimates and 90% CIs for the “test/reference” geometric mean ratios of these parameters will be provided. The primary PK parameters that will be used for the bioequivalence assessment are  $C_{max}$  and  $AUC_{0-t}$ . All other PK-related assessments of equivalence will be considered secondary.

Any missing samples or non-reportable concentration values will be disregarded in the PK analysis.

If terminal phase of serum concentration-time profile has sufficient data points, apparent terminal elimination half-life ( $t^{1/2}_{1/2}$ ), apparent terminal elimination rate constant ( $\lambda_z$ ), mean residence time (MRT), clearance (CL/F), and volume of distribution (V/F) will be calculated.

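### With no PK sample between 5 h and 10 h, the SAP's linear-down rule misstates the secondary AUC6-12h; the primary AUC0-t also carries two definitions

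*SAP*

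**What the plan says.** The Protocol synopsis lists the later insulin samples at "135, 150, 180, 210, 240, 300, 600, and 720 minutes post-dose". SAP Table 4.2 gives the same times. After 5 h the next samples are therefore at 10 h and 12 h.

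SAP 22.2 states that parameters are derived "using linear up/ linear down non-compartmental analysis (NCA". Table 22.2 there includes AUC6-12h, described as "concentration-time curve from 6 to 12 hours". SAP 3.2 names AUC6-12h and AUC0-6h as secondary endpoints under "PK parameters for serum insulin aspart concentrations". No sample is scheduled at 6 h, and the SAP does not say how the 6-h concentration is to be obtained.

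The SAP has no explicit rule for using values below the limit of quantification (BLQ) in the non-compartmental analysis. Section 22.1 says "For geometric statistics, imputed BLQ values of zero will be omitted", which implies zero imputation but speaks only to geometric statistics. Section 22.4 says "Any missing samples or non-reportable concentration values will be disregarded in the PK analysis".

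The primary AUC0-t is labelled "Aspart concentration-time curve from 0 to 12 hours" in SAP 3.1, whereas SAP Table 22.2 defines it as "concentration-time curve from 0 hour to the last quantifiable concentration time".

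**The concern.** A straight line drawn across five hours of a declining concentration curve lies above the curve, so the area under it is too large. AUC6-12h starts one hour into that gap, so much of what is reported for 6–12 h is the 5-h sample carried forward along the line.

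The secondary PK objective is to compare additional parameters with each reference. A difference in late exposure is what AUC6-12h should reveal, and an area driven by the 5-h sample responds to it only weakly. In a similarity trial, an error that moves a ratio toward 1 favours the sponsor's conclusion.

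The same gap matters for AUC0-t under the Table 22.2 definition. If the 10-h value is BLQ and no later value is quantifiable, AUC0-t ends at 5 h; the curve cannot end anywhere between 5 h and 10 h.

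**Working it through.** **Inputs.** From the documents: samples at 5, 10 and 12 h (Protocol synopsis, SAP Table 4.2); linear trapezoids on both limbs (SAP 22.2); a 6–12 h window (SAP Table 22.2). Not in the documents, hence assumed: half-life 1 to 3 h, Tmax 50 to 75 min, and any limit of quantification (LLOQ). Nominal times are used. The plan states no figure on this point to reproduce.

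**Step 1: what the rule computes.** Write C5, C10, C12 for the three samples.
- C(6h) = 0.8·C5 + 0.2·C10.
- 6–10 h: 4 × (C(6h) + C10)/2 = 1.6·C5 + 2.4·C10.
- 10–12 h: 2 × (C10 + C12)/2 = C10 + C12.
- Sum: AUC6-12h = 1.6·C5 + 3.4·C10 + C12.

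**Step 2: error in level.** For exponential decline with k = ln 2 / half-life, C10/C5 = exp(−5k), C12/C5 = exp(−7k), and the true area is C5·(exp(−k) − exp(−7k))/k. With C5 = 1:

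| Half-life | C10 | C12 | Linear | True | Error | Share from 5-h sample | Only 6-h value log-interpolated | C10 and C12 set to 0 |
|---|---|---|---|---|---|---|---|---|
| 3 h | 0.315 | 0.198 | 2.87 | 2.58 | +11% | 56% | +6% | −38% |
| 2 h | 0.177 | 0.088 | 2.29 | 1.79 | +28% | 70% | +14% | −10% |
| 1.5 h | 0.099 | 0.039 | 1.98 | 1.28 | +55% | 81% | +25% | +25% |
| 1 h | 0.031 | 0.008 | 1.71 | 0.71 | +141% | 93% | +55% | +125% |

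Example at 2 h: 1.6 + 3.4 × 0.177 + 0.088 = 2.29, and 2.29/1.785 = 1.28. The last column is 1.6·C5 divided by the true area.

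One-compartment profiles with first-order absorption and Tmax 50–75 min give +11%, +28%, +53–55% and +108–141%. The lower end at 1 h arises because absorption still contributes after 5 h. On the same profiles, log interpolation to 6 h followed by log trapezoids is within −4% to 0% of the true area.

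**Step 3: error in the ratio.** If test and reference have the same shape, both areas carry the same factor and the ratio is exact. Now let the reference half-life be 1.5 h and the test half-life 10% longer, with equal total AUC, the same absorption rate and the 10-h sample quantifiable. A true ratio of 1.20–1.24 is then reported as 1.12–1.15. In the other direction, with equal C5 and half-lives of 1.5 h (test) and 1.8 h (reference), 0.80 is reported as 0.91.

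**Step 4: BLQ values.** If 10-h and 12-h values are BLQ and set to zero, the formula collapses to 1.6·C5, and the last column of the table shows that the sign depends on the half-life. The ratio behaves likewise. Simulated with a 10% longer test half-life and zeros for BLQ, a true 1.075 at 3 h is reported as 1.09–1.11 when 10–50% of reference profiles are BLQ at 10 h. At 2 h with 50% BLQ, a true 1.157 is reported as 1.153.

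**Step 5: other parameters.** Cmax does not use the gap. AUC0-6h is off by about 1% at most, because only its last hour falls in the gap. For AUC0-t as Table 22.2 defines it, ending at 10 h rather than 5 h raises the value by 9–17% (half-life 1 h), 18–23% (1.5 h) or 26–30% (2 h).

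**The case against.** The strongest reply is that nothing turns on AUC6-12h. SAP 22.3 and 22.4 apply the models and the 80–125% range to Cmax and AUC0-t. SAP 22.4 calls other equivalence assessments secondary and gives them no range. Half-life and t50%-late are also planned and bear on late decline. The level error is common to all three products if their profiles are alike, and the ratio examples need a postulated half-life difference. This stands, and it limits the weight of the point.

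The second reply is that the size is assumed. Without a half-life, 11% to 141% fixes little beyond direction, and the SAP does not say that the 6-h value is linearly interpolated. This stands in part. Log interpolation of that value alone still leaves +6% to +55%, because the trapezoids stay linear. Slower absorption also shrinks the error: an absorption half-life of 0.75 h gives about 10%, 25% and 47% at 3, 2 and 1.5 h, but puts Tmax at 90 to 120 min.

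Three stronger readings are tempting, and the documents do not support them.
- *AUC6-12h is always overstated.* This needs a quantifiable 10-h sample; zeros for BLQ can turn it into an understatement.
- *The ratio is always pulled toward 1.* This has the same condition, and Step 4 shows exceptions.
- *The primary PK comparison is underpowered.* A case can be built: at CV 26%, ratio 0.95 and 36 evaluable, simulated power is 87–88% without the 5-h/10-h step and 66–68% at half-life 2 h with an LLOQ of 5% of Cmax. That pairing is the least favourable tested, and the documents give no LLOQ. Protocol Table 9 puts the AUC0-t CV lower (mean 21.7%, median 17.0%). If AUC0-t means 0 to 12 h with BLQ as zero, simulated power stays at 84–88%.

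**Conclusion.** The point holds for the secondary AUC6-12h. The sampling gap and the linear-down rule are both written in the plan, and neither SAP 22.1, the reliability criteria in 22.2 nor 22.4 corrects the result. Provided the 10-h sample is quantifiable and the 6-h value is linearly interpolated, the overstatement is about 11% to 141% over assumed half-lives of 3 to 1 h. The ratio is exact for equal shapes and attenuated when late declines differ. Where late values are BLQ and zeroed, the direction is not general.

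The two definitions of AUC0-t are a separate, real inconsistency in a primary parameter. Reading it as 0 to 12 h also makes it duplicate AUC0-12h, which SAP 3.2 lists as secondary. Any power cost is not established. No acceptance decision rests on AUC6-12h, so this is a change to consider rather than a threat to the trial's conclusion.

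**What to change.** In SAP 22.2 add:

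*For AUC6-12h, the 6-h concentration is obtained by log interpolation, and declining segments after 5 h between quantifiable samples are integrated by the log trapezoidal rule. Where no quantifiable sample follows 5 h, AUC6-12h is listed and not summarised, and the number of such profiles is reported by treatment.*

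Keep the linear rule for AUC0-t, AUC0-12h and AUC0-6h. State one BLQ rule for the non-compartmental analysis in 22.1 and refer to it in 22.4. One workable form: a BLQ value after the last quantifiable sample is zero for AUC0-12h and is not used for AUC0-t; a BLQ value between quantifiable samples, or any missing or non-reportable value, is treated as missing. Reconcile SAP 3.1 with Table 22.2 on AUC0-t, and report the already planned AUC0-12h through the primary PK models as supportive.

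The cost is SAP text before database lock and one additional model run; sampling and conduct do not change. There are three downsides:
- The log rule assumes exponential decline across hours that remain unobserved.
- The partial areas will not add exactly to the linear AUC0-12h. At a half-life of 2 h, where AUC6-12h is about 13% of the true total, the gap is roughly 0.28 × 13% ≈ 3.6% of that total.
- Profiles left out for BLQ are the faster-declining ones, so any AUC6-12h ratio should be read alongside the counts by treatment.
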